7.4 Subject Withdrawal Criteria

If a subject fails to return for a scheduled study visit, the investigator will make a reasonable effort to contact the subject and determine why the subject failed to return and to schedule a new study visit. Any information obtained during this contact will be documented in the study records.

A study subject will be discontinued from treatment in the study if:

- Any clinically significant AE, laboratory abnormality, illness, or other medical condition or situation occurs such that continued participation in the study would not be in the best interest of the subject.
- OxThera or the Principal Investigator in consultation with OxThera may discontinue the subject at any time for medical and/or administrative reasons.
- The Prinicpal Investigator in consultation with OxThera may discontinue the subject in case of a major protocol violation.
- The subject requires dialysis.

Protocol OC5-OL-02, Confidential

Any subject who withdraws prematurely from the study treatment will be asked to complete all study assessments scheduled for the month 12 or 24 visit at the time of withdrawal and will be followed for safety for 4 weeks after the last intake of study drug. Subjects will provide a stool sample 4 weeks after end of treatment.

Patients who withdraw consent from participating in the study at any time will end the study. They will not have any further assessment and no further study data will be collected.

For any subject who has withdrawn, the date of withdrawal from the study and the reason for withdrawal from treatment and from the study will be recorded in the source data and eCRF.

Withdrawn subjects will not be re-entered into the study.

8 TREATMENT OF SUBJECTS

8.1 Description of Study Treatment

The study drug consists of Oxabact OC5 as the active treatment. The study drug is supplied as enteric-coated size 4 capsules. One capsule shall be administered orally with water twice daily with breakfast (in the morning) and dinner (in the evening). The study product is described in more detail in section 9.

8.2 Concomitant Medications

Any medications including over-the-counter medications or herbal supplements will be recorded as concomitant drug therapy on the case report form. Prior/concomitant medication used in the 60 days prior to signing of the ICF will be recorded as part of the ePHex study documentation. If a seamless transition (delay >1 month) from the ePHex study to the ePHex-OLE study should not be possible, information on medication used from completion of the ePHex study to first dosing in the ePHex-OLE study will be recorded. Any historical use of vitamin B6 and any other relevant medication as judged by the investigator should also be recorded. Subjects may continue any medications they are receiving at study entry for underlying medical conditions. The medications will be recorded at screening of the ePHex study and changes will be noted throughout the study.

8.2.1 Concomitant Treatment with Vitamin B6

Subjects who had received vitamin B6 (pyroxidine) during the ePHex study should maintain a stable dose. Subjects not receiving vitamin B6 during the ePHex study must be willing to refrain from initiating pyridoxine during participation in the ePHex-OLE study. Subjects will be encouraged not to change the dosing of vitamin B6 or discontinue vitamin B6 during study participation except for any safety events considered related to vitamin B6.

8.2.2 Prohibited Medications

Prohibited medications are:

- Ascorbic acid preparations: Ascorbic acid preparations must not be used during the study period as it may affect the measurement of urinary oxalate.
- Long-term use of antibiotics: Subjects that require long-term use (more than 3 consecutive weeks) of antibiotics to which *O. formigenes* is sensitive during the treatment period will discontinue study drug and be followed for safety.
- For subjects that require short-term use of antibiotics during the treatment period, care should be taken to primarily choose antibiotics to which *O. formigenes* is resistant. In case of repeated short-term use (more than one course) an evaluation will be made to assess the risk for interference with the study drug treatment.
 - O. formigenes has shown resistance to antibiotics that affect the cell envelope, such as ceftizoxime, imipenem, ampicillin, amoxicillin and penicillin.

 O. formigenes has shown sensitivity to antibiotics that are protein synthesis inhibitors, such as chloramphenicol, doxycycline, erythromycin, and tetracycline.

8.3 Treatment Compliance

Compliance to study treatment will be checked with the subject at each visit to the clinic. Any missed doses or doses lost during handling should be registered in the eCRF and/or source documentation.

Unused medication will be returned to the clinic or site pharmacy at the next clinical visit, or the visit thereafter if new supply has not yet been received by the subject. Accountability will be done at the hospital pharmacy based on dispensed and returned drug for an overall check of subject compliance.

8.4 Open-label

Subjects will be identified with a unique identification number consisting of country and site identification number and consecutive subject number which they had been assigned at the first screening visit of the ePHex study. Subjects will receive study drug in an open-label manner.

9 STUDY DRUG MATERIALS AND MANAGEMENT

9.1 Study Drug

OC5 is supplied as enteric-coated, size 4, gelatine capsules. One capsule contains NLT 10^9 CFU and has the capacity to metabolise NLT 100 mmol oxalate per 19 hours. Details on the product are described in Table 7 below:

Table 7 Details of the Study Drug in the ePHex-OLE Study

Parameter	High Dose
Active Substance	Lyophilised O. formigenes , strain HC-1
Name	Oxabact (OC5)
Route of Administration	Oral
Dose form	Enteric-coated capsule
Viable cell count	1.0 * 10 ⁹ – 5.0 * 10 ¹⁰ CFU/dose
Oxalate degrading capacity	>100 mmol/capsule
Excipients	Oligofructose, maltodextrin, alginate, sucrose, microcrystalline cellulose

9.2 Study Drug Packaging and Labelling

Capsules will be filled into sealed aluminium tubes. Each tube will initially contain 18 capsules. During the course of the study, there will be a transition from tubes containing 18 capsules to tubes containing 16 capsules. The overage medication in each tube will be reduced from 4 to 2 extra capsules in each 2-week supply.

The label, including subject number, will be placed on the aluminium tube and on secondary packaging (transparent bag) holding the aluminium tubes.

The product will be labelled to meet national regulatory requirements.

9.3 Study Drug Storage

Study medication provided by the sponsor must be stored in a temperature-controlled freezer (-20°C +/- 5°C), in a locked area at site pharmacies before dispensing and delivery to patients. Study medication should be stored refrigerated (2°C to 8°C) at the subject's home, current stability data supports up to 4 weeks refrigerated storage.

9.4 Study Drug Accountability, Handling and Disposal

 $\mbox{OxThera}$ will supply study medication through the designated drug depot to all sites in the study.

The drug depot will complete a drug inventory log to document receipt and distribution of study drug. They will send study drug to the site pharmacies as a controlled shipment at -20°C +/- 5°C . The site pharmacies will store study medication in a temperature-controlled freezer (-20°C +/- 5°C), in a locked area. The site pharmacies will distribute study drug to subjects and will inform subjects that study capsules should be stored

refrigerated (2°C to 8°C) at their homes in the securely sealed tubes. Subjects will be supplied with sufficient capsules for dosing every second week.

Unused study medication and empty vials will be returned by the subject to the clinic or site pharmacy at the next scheduled visit to the clinic after each delivery of new supply. The pharmacy will document receipt of unused study medication. Any surplus of study medication will be reviewed and properly documented by the study monitor, and returned to the distributor.

Investigational product accidentally destroyed in transit, in subject's home or at the study site should be accounted for and documented.

10 ASSESSMENT OF EFFICACY

The efficacy parameters to be assessed are:

Primary Endpoint

Change from baseline in kidney function (eGFR) after 12 and 24 months of openlabel Oxabact treatment.

Key Secondary Endpoints

- Change from baseline in total plasma oxalate concentration after 12 and 24 months of open-label Oxabact treatment
- ❖ Frequency of kidney stones events after 12 and 24 months of open-label Oxabact treatment. Kidney stone events are defined as:
 - o Subject- or investigator-reported symptoms, or
 - Stone passages or removals, or
 - o Increase in the number of kidney stones as assessed by ultrasound.

Other endpoints

- Change from baseline in myocardial function parameters as measured by Speckle Tracking and traditional echocardiography
- ❖ Change from baseline in free plasma oxalate concentration
- Change from baseline in urinary oxalate excretion
- Change from baseline in grade of nephrocalcinosis as assessed by ultrasound
- **\Delta** Change in number of *O. formigenes* in stool
- ❖ Association between change in number of *O. formigenes* in stool and change in total plasma oxalate concentration
- ❖ Change from baseline in score of Quality of Life questionnaire.
- Change from baseline in markers for renal function, renal tubular capacity and inflammation:

Urine: magnesium, phosphorus, citrate, calcium, glycolate, creatinine, urea, calcium oxalate crystals, pH, osmolality and urinary volume. *Blood*: magnesium, phosphorus, citrate, calcium, BUN, ALP, bicarbonate, CRP, WBC, creatinine and cystatine C.

10.1 Kidney Function Parameters

Samples for eGFR calculations will be processed at the clinical site and analysed at a central lab (BARC). Each site will be provided with kits and supplies for collection, processing and shipping of blood samples for determination of serum creatinine and cystatine C. Complete instructions for the collection, processing, storage and shipping of sample will be provided in the site manual.

10.2 Kidney Stone Events

Kidney stones are hard deposits made of minerals and salts that form inside the kidneys. Most kidney stones (approximately 80%) are calcium stones, usually in the form of calcium oxalate. Stones can also be composed of struvite, uric acid or cystine. Stones vary in size and shape, ranging from a few mms up to 40 mms. Patients can typically pass the smaller stones in the urine. However, larger stones (e.g. >10mm) may require lithotripsy and surgical or endoscopic removal. A kidney stone may not cause symptoms until it moves around within the kidney, passes into the ureter, bladder, or urethra.

Stone Events

In this study, kidney stone events are defined as follows:

- A stone event could be defined as the occurrence of one of the following symptoms due to a kidney stone that may or may not require medical intervention:
 - Abdominal, flank or groin pain, sometimes associated with nausea and vomiting.
 - o Macroscopic hematuria (visible blood in the urine).
 - Urinary tract infection (cloudy or foul-smelling urine, more frequent and/or painful urination than normal, persistent need to urinate and/or urinating small amounts).
- Stone events may also be defined by subject-reported stone passage or by medical procedures to remove identified kidney stones (e.g. lithotripsy, endoscopy, surgery).
- An increase in number of kidney stones as seen in a kidney ultrasound would also be classified as a stone event.

Duration between stone events: if symptoms of a stone event occur simultaneously or close in time to another kidney stone event, the investigator can decide whether or not this should be reported as a separate stone event.

Assements of kidney stone events will be collected by ultrasound (renal imaging) (see section 10.6.2 below) as well as subject-reported stone events or symptoms of events (see definition above). Historical kidney stone events and related symptoms for the past three years preceding study entry will be asked at baseline of the ePHex study. During the study period of the ePHex-OLE study, information will be collected concerning occurrence of self-reported kidney stone event and related symptoms. This information will be captured by completing the applicable items on the Adverse Event eCRF. (Please note this is a data entry convention only and does not replace the per protocol definition of an Adverse Event as defined in Section 11.1).

10.3 Plasma Oxalate

Samples for plasma oxalate will be collected during each clinical visit (i.e., every two to three months).

Samples for total plasma oxalate will be processed at the clinical site and analysed at Academic Medical Center (AMC), Amsterdam, the Netherlands. Each site will be provided with kits and supplies for collection, processing and shipping of blood samples

for determination of total plasma oxalate. Complete instructions for the collection, processing, storage and shipping of sample will be provided in the site manual.

Total plasma oxalate will be measured using isotope dilution gas chromatography with mass selective detection (GC-MSD).

Ultrafiltered, acidified plasma samples will also be analysed for free plasma oxalate with GC-MSD at AMC.

The ratio between the two different results will be monitored throughout the study.

Earlier studies on Oxabact used either an enzymatic assay for plasma oxalate where the oxalate available for enzymatic reaction is measured, or a standard plasma oxalate Ion Chromatography (IC) method where a 10 kDa ultra filtration step prior to acidification of the sample separates the protein-bound oxalate from the sample. Earlier study results should therefore be interpreted with this fact in mind. In contrast, since the sample preparation for analysis of total plasma oxalate does not include an ultra filtration step prior to acidification, the method measures the total amount of plasma oxalate. Since the major portion of the plasma oxalate is likely protein-associated (Hatch, 1990; Hatch *et al.*, 1977) both ultrafiltered samples and samples without ultrafiltration will be analysed in the ePHex-OLE study, complementary to each other. By using both sample preparation methods in the study for analysis of plasma oxalate, the ratio between the change in free plasma oxalate and the change in total plasma oxalate can be evaluated as an indicator of change in protein-associated oxalate, as well as the two different parameters independently.

10.4 Speckle Tracking and Traditional Echocardiography

Speckle Tracking Echocardiography (STE) is currently evaluated as a method to detect and quantify effects of oxalate deposits in the heart muscle (Lagies *et al.*, 2013; Lagies *et al.*, 2019). STE is considered to be a feasible tool for discovering subtle changes of myocardial performance and identifying PH patients at risk for serious cardiac damage.

Speckle Tracking and traditional echocardiography will be performed four times during the treatment period. The examination will be performed locally using specific equipment as detailed in the site manual. Images will be interpreted centrally in a blinded manner. If the images are not meeting the quality criteria, the examination will be repeated within 4 weeks of the initial examination (except for visit 10).

Complete instructions for the collection, processing, storage and transfer of images will be provided in the imaging manual.

STE evaluations will include global longitudinal strain, including segmental changes, short-axis myocardial function, rotational displacement and apical sparing patterns. Traditional echocardiographic parameters will also be evaluated (e.g. Ejection Fraction, End Diastolic Volume, e/é, e/a, Left Ventricular End Diastolic Dimension, Fractional shortening, Tricuspid Regurgitation by Doppler as an indicator of right ventricular/pulmonary pressure.

10.5 Quality of Life Questionnaire

A questionnaire will be used to evaluate the Quality of Life for the participating subjects. The SF36v2 questionnaire will be used for the adult subjects (18 years or older) and the CHQ/PF50 for subjects aged 5-<18 years and their parents (per age at the ePHex-study

entry). The same questionnaire will be completed by the subjects/parents during the clinical visits at months 6, 12, 18 and 24.

10.6 Other Parameters for Evaluation of Treatment Effect

10.6.1 Quantification of *O. formigenes*

The possibility to monitor the natural occurrence of *O. formigenes* bacteria and the presence of the *O. formigenes* drug before, during and after treatment with OC5 is an important tool for control of the pharmacodynamics of the drug. To date, two different genotypes of naturally occurring *Oxalobacter formigenes* have been identified, genotype 1 and 2 (groups I and II). Oxabact, or OC5, is of the strain HC-1 of the *O. formigenes* genotype 1. A real-time quantitative PCR assay will be used that permits determination of the numbers of both *O. formigenes* genotype 1 and genotype 2 in faecal samples.

Faecal samples will be collected at the subject's home and shipped to central laboratory MVZ Institut für Mikroökologie GmbH, Herborn, Germany.

A positive treatment effect on the result from analysis of number of *O. formigenes* should show an increased number of *O. formigenes* genotype 1 during treatment period. Earlier studies have shown that *O. formigenes* genotype 2 have increased in the OC5 treated group, but not in the placebo group indicating a transfer of oxalate from plasma to the intestine mediated by OC5 treatment. *O. formigenes* genotype 2 will also be monitored for this reason.

10.6.2 Ultrasound

Ultrasound of the kidneys will be done at the site hospital. Images will be sent for central reading in a blinded manner. The examination will be standardised and described in detail in the imaging manual.

Ultrasound images will be evaluated to determine the grade of nephrocalcinosis and the amount of kidney stones.

For nephrocalcinosis, the grading system using the ultrasound will be using 0-3 grades according to reference article published by Boyce *et al.*, (Boyce *et al.*, 2013):

- Grade 0: no echogenicity
- Grade 1: mild echogenicity around medullary pyramid borders
- Grade 2: moderate echogenicity around and inside pyramids
- Grade 3: severe echogenicity of entire pyramids

10.6.3 Twenty-four Hour Urine Samples

Twenty-four-hour urine samples for analysis of urinary oxalate, calcium, glycolate, magnesium, citrate, urea, creatinine, phosphorus excretion, pH, osmolality and urine volume will be taken at patient's home and sent to central laboratory TDL, London, UK. Urine calcium oxalate crystals and pH will also be analysed from this sample. Urinary oxalate will be analysed with a colorimetric enzymatic assay using oxalate oxidase,

which oxidizes oxalate to carbon dioxide and hydrogen peroxide. The analyses will be described in more detail in the lab manual.

10.6.4 Plasma Sample - Other Endpoints

Plasma samples will also be analysed for magnesium, phosphorus, citrate, calcium, BUN, ALP, bicarbonate, CRP, WBC, creatinine and cystatine C. The details of sampling and analysis of these parameters will be outlined in the lab manual.

11 ASSESSMENT OF SAFETY

The safety parameters to be assessed are:

- Adverse Events
- Laboratory safety measurements
- Vital signs
- Physical examination

11.1 Definition of Adverse Events

Adverse Event (AE)

An AE is any untoward medical occurrence in a patient or clinical study subject administered a pharmaceutical product and which does not necessarily have a causal relationship with this treatment. An AE can therefore be any unfavourable and unintended sign (including abnormal laboratory finding), symptom, or disease temporally associated with the use of a medicinal (investigational) product, whether or not related to the medicinal (investigational) product. AEs therefore include e.g. worsening of a pre-existing illness and any injury or accident. This refers also to symptoms due to a pre-existing allergy, e.g. if seasonal allergy symptoms are within what is normally experienced, then they should not be recorded as AEs. If the symptoms are worse than what is normally experienced, then they should be recorded as AEs.

An AE does **not** include:

- Symptoms of the underlying disease (with the exception of kidney stone events) that might be reasonably anticipated to come and go, or progress, given the nature and severity of the condition. However, if the progression of the disease escalates resulting in hospitalisation, is life-threatening, or is fatal, then progression of the disease should be reported as an AE of serious nature;
- Expected variations in severity of disease signs and symptoms that have previously been reported in the subject's medical history;
- Pre-planned medical or surgical procedures (e.g., surgery, tooth extraction, or transfusion) [Note: The condition that leads to the procedure may be an AE];
- Overdose of study drug without any clinical signs or symptoms; or
- Clinically significant laboratory values. If abnormal laboratory values are accompanied by abnormal signs or symptoms, the signs or symptoms are considered an AE and should be recorded as such. Abnormal laboratory values associated with the underlying

disease are not an AE unless the values unexpectedly worsen. Abnormal laboratory values will be recorded in the study database.

Adverse Drug Reaction (ADR)

An AE is defined as an adverse drug reaction (ADR) if further analyses prove that the AE is caused or partially caused by the investigational product. This includes interaction, overdosing, abuse and development of addiction. Expected ADRs are also possible events due to the substance class of the investigational drug, expected from analogue conclusions or theoretical considerations related to toxicological, pharmacological or kinetic characteristics.

Serious Adverse Event (SAE)

A Serious Adverse Event (SAE) is one that suggests a significant hazard, contraindication, side effect or precaution that results in:

- Results in the subject's death
- Is life-threatening*
- Requires inpatient hospitalisation or prolongation of existing hospitalisation**
- Results in persistent or significant disability/incapacity; or
- Results in congenital anomaly/birth defect
- corresponds to another important medical event as determined by the Investigator.
 - * Life threatening means that the subject was at immediate risk of death from the AE as it occurred, or it is suspected that the use or continued use of the investigational product would result in the patient's death. Life threatening does not mean that had an AE occurred in a more severe form it might have caused death.
 - ** Hospitalisation requires overnight stay at the hospital. Outpatient treatment in an emergency room is not itself a SAE. Hospital admission and/or operations planned before or during a study are not considered SAEs if the illness or disease existed before the patient was enrolled in the study, provided that it did not deteriorate in an unexpected way during the study.

Suspected Unexpected Serious Adverse Reaction (SUSAR)

Suspected Unexpected Serious Adverse Reaction (SUSAR) is a suspected unexpected serious adverse reaction.

In cases of doubt on this issue, it is suggested that there should be a predisposition to report rather than not to report (see section 11.3).

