11.5.5 Elevated Levels of Plasma Formate

Since *O. formigenes* converts oxalate to formate in the intestine, there may theoretically be a possibility of elevated plasma formate levels following administration of high doses of OC5. However, formate is metabolised by a number of bacteria in the gut microbiota. Formate is a metabolite of methanol responsible for the toxicity observed with methanol poisoning. Typically, toxic effects require prolonged exposure to elevated plasma formate levels.

The potential for elevated plasma formate levels following administration of OC5 is theoretically limited due to the limited availability of endogenous oxalate. Over 100 subjects have been exposed to date to Oxabact (OC3 and OC5) with doses up to NLT 109 CFU in studies up to 36 months. There have been no signs or symptoms of elevated formate plasma levels, metabolic acidosis or methanol poisoning. The main manifestations of methanol poisoning are metabolic acidosis and ocular toxicity. Any subject who develops signs and symptoms of metabolic acidosis should be evaluated to identify the source (e.g. evaluation of serum bicarbonate, blood pH, anion gap, osmolality gap and/or plasma formate).

Formate accumulation in plasma is the main reason for acidosis in early, uncomplicated stages of metabolic acidosis. Metabolic acidosis is characterised by low blood pH (arterial pH <7.38 or venous pH <7.34) or low levels of serum bicarbonate, HCO $_3$ (<18 mmol/L). Decreased levels of serum bicarbonate or blood pH will serve as an indication of elevated levels of formate. The ePHex study will investigate these early signs of elevated plasma formate as part of routine safety labs. Low levels of serum bicarbonate should trigger determination of the anion gap and the osmotic gap in order to confirm or rule out the diagnosis of metabolic acidosis due to elevated formate levels.

If metabolic acidosis is diagnosed, the acidosis should be corrected as quickly as possible and therapy provided, if appropriate. If a diagnosis due to elevated formate levels cannot be excluded or if the metabolic acidosis cannot be corrected by standard of care the study medication should be stopped until further evaluation. Further evaluation should then include levels of plasma formate and visual disturbance test.

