7.7.2 Clinical laboratory

The following laboratory safety data are collected for this study:

Haematology	Chemistry	Urinalysis
RBC (Erythrocytes)	Blood Urea Nitrogen	Protein
WBC (Leucocytes)	Electrolytes (Na ⁺ , K ⁺ , Mg ⁺⁺ , Ca ⁺⁺ , HCO ₃ ⁻ , Cl ⁻)	Glucose
Lymphocytes	Glucose	pH
Monocytes	Albumin	
Neutrophils	Alkaline phosphatase	
Basophils	ALT	
Eosinophils	AST	
Platelets	Total bilirubin	
Haemoglobin		
Haematocrit		
MCV		
MCHC		

Urine 24h measurements are already presented as ‘Other endpoints’ markers for renal function, renal tubular capacity and inflammation (see section 7.6.3).

Laboratory safety data for haematology, biochemistry and urinalysis will be summarized using descriptive statistics for values over time, change from baseline and percent change from baseline per visit and treatment group/overall, using protocol visits. Listings will include the change from baseline values.

Safety laboratory parameters are collected both in conventional units and SI units: SI units will be used in the tabular presentations.

Lastly, for clinical laboratory parameters, a listing will be created presenting all data that are out of reference range on a per-subject level, including any available unscheduled measurements. The investigator has judged the out-of-range values on their clinical significance, and this information will be added as well. Information regarding age at screening and gender will be added to this listing.

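### Protocol 11.1 both includes and excludes clinically significant laboratory abnormalities as adverse events, so new, symptom-free ones may be counted inconsistently or not at all

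*Protocol*

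**What the plan says.** Protocol 11.1 begins broadly: "An AE can therefore be any unfavourable and unintended sign (including abnormal laboratory finding), symptom, or disease". A list introduced by "An AE does not include" follows. Its last bullet reads "Clinically significant laboratory values", with no qualifying word.

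The rest of that bullet adds three things:

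- Where an abnormal value comes with signs or symptoms, "the signs or symptoms are considered an AE and should be recorded as such".
- Abnormal values associated with the underlying "disease are not an AE unless the values unexpectedly worsen".
- "Abnormal laboratory values will be recorded in the study database".

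On the analysis side, SAP 7.7.1 builds the treatment-emergent AE (TEAE) tables from reported AEs. SAP 7.7.2 summarises safety laboratory data by visit and treatment group. It adds a per-subject listing of out-of-range results, for which it says "The investigator has judged the out-of-range values on their clinical significance".

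**The concern.** Safety is the only secondary objective (Protocol 5.2). AE tables are the main way safety is counted, graded and attributed to treatment. If the definition points both ways for one class of finding, an investigator who follows the opening paragraph and one who follows the exclusion bullet will record the same result differently, and both will be within the protocol.

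Causality and intensity are recorded for AEs (Protocol 11.3). A laboratory value kept off the AE page therefore gets neither.

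The study is small: SAP 2.4 gives 18 included subjects. A few events classified differently would visibly change the incidence tables. Protocol 11.10 designates no monitoring board for this study. The parent study's board covers these subjects only until that study is completed.

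**Working it through.** No arithmetic underlies the contradiction, and the plan gives no figure to reproduce. The check sets the passages side by side.

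**Step 1. Apply both parts of Protocol 11.1 to each kind of laboratory abnormality.**

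| Case | Opening definition | Exclusion bullet | Result |
|---|---|---|---|
| Abnormal value with signs or symptoms | Can be an AE | The sign or symptom is the AE | Counted, as the symptom |
| Disease-associated value, worsens unexpectedly | Can be an AE | AE | Consistent |
| Disease-associated value, no unexpected worsening | Can be an AE | Not an AE | An explicit exception for background disease |
| New, symptom-free, clinically significant value not explained by the disease | Can be an AE | Not an AE | Contradiction |

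The third row is a recognisable carve-out. The fourth is not. A raised ALT is an example, since ALT is in the safety panel of Protocol 11.6. The only explicit route back for a symptom-free value is reserved for disease-associated values. As written, the exclusion is therefore strictest where the disease offers no alternative explanation.

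**Step 2. See whether other protocol sections settle it.**

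- 11.2, Table 8, words five of its six causality categories for an event or a laboratory test abnormality.
- 11.3 names laboratory results as a source of AE information, and its Grade 1 covers symptom-free findings that are diagnostic observations only.
- 7.4 gives a clinically significant laboratory abnormality as a ground for discontinuing treatment.

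Sections 11.2 and 11.3 assume that a laboratory abnormality can be an AE, and 7.4 treats one as important enough to end treatment. None of them overrides the bullet.

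**Step 3. See whether the SAP restores the count.** The tables of TEAEs, grade, relatedness and discontinuation in 7.7.1 use reported AEs. Section 7.7.2 plans descriptive statistics, changes from baseline and the out-of-range listing, but no table of the number of subjects with values judged clinically significant. Section 7.6.3 also takes the renal and inflammation markers out of the safety laboratory summaries and presents them on the Full Analysis Set. Six blood tests appear both there and in the 7.7.2 safety panel: bicarbonate, BUN, ALP, WBC, magnesium and calcium.

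**Step 4. Exposure.** The schedule has safety laboratory tests at 11 visits, Visits 0 to 10. Visit 0 precedes the first open-label dose, and AE reporting starts with study treatment (Protocol 11.4). So 11 − 1 = 10 scheduled visits per subject can yield a TEAE. With 18 subjects the ceiling is 18 × 10 = 180 subject-visits. That is a count of opportunities, not of expected events. The documents give no rate of clinically significant values.

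**The case against.** The strongest reply is that little is lost. Values are kept in the database and summarised by visit, and out-of-range results are listed with the investigator's judgement. With 18 subjects, a reader could count the flagged cases by hand. The markers moved by SAP 7.6.3 are still summarised per visit, on the Full Analysis Set. All of this stands. It limits the point to AE tabulation, because a listing carries no causality assessment and does not feed the TEAE tables.

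Stronger readings are tempting, but the documents do not support them:

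- **That only symptoms can make a laboratory finding an AE.** The bullet keeps disease-associated values that worsen unexpectedly.
- **That the protocol's own formate marker would go unseen.** Protocol 11.5.5 says "Decreased levels of serum bicarbonate or blood pH will serve as an indication of elevated levels of formate", and a reader might infer that a silent low bicarbonate would vanish. The same section requires further work-up of a low value. A diagnosed acidosis would be a disease under the opening definition. Bicarbonate is also listed among the renal and inflammation markers, so a site could treat unexpected worsening as disease-associated. Bicarbonate illustrates the ambiguity, not a certain loss.
- **That such values will certainly be missing, including from the tables of serious events.** Sections 11.2 and 11.3 may lead some sites to report them anyway, and 11.1 lets the investigator classify an important medical event as serious. The supportable claim is that recording may differ between sites and that some values may be absent.

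The bullet may be a drafting slip. The documents do not show what was intended, and sites have to work from the text as it stands.

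**Conclusion.** The point holds as an internal contradiction in the AE definition with a limited consequence. A new, symptom-free, clinically significant laboratory value that the disease does not explain is an AE by one sentence of Protocol 11.1 and not by another. No other text in either document clearly resolves it. Such values may be recorded differently between sites, and may be absent from the TEAE and relatedness tables. If a subject stops treatment because of one, it may also be absent from the discontinuation table.

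The number of events affected cannot be estimated. The bound is 10 post-dose scheduled laboratory visits per subject. The conclusion rests on reading the bullet literally and on the TEAE tables being built only from reported AEs, as SAP 7.7.1 describes. The laboratory data remain available. The point is worth correcting because safety is the sole secondary objective and the remedy is small.

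**What to change.** 1. **Protocol.** Reconcile the opening paragraph and the last exclusion bullet of 11.1 with each other and with 7.4, 11.2 and 11.3. One way is to limit the exclusion to laboratory values judged not clinically significant. The SAP indicates that investigators already make this judgement for out-of-range results, so no new assessment is needed.
2. **SAP, whichever rule is kept.** Add a table on the Safety Analysis Set, by treatment group and overall, counting subjects with laboratory values that the investigator judged clinically significant. Include bicarbonate and the other markers that 7.6.3 moves out of the safety summaries. This uses flags already collected and needs no protocol change.

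Cost: the protocol change needs ethics committee and regulatory approval (Protocol 19) and would arrive part-way through a study with subjects already included. Unless earlier laboratory results are reviewed again, the clarified rule would apply only from then on, and the report should say so. Somewhat more AEs would be recorded. The SAP change costs one table.
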